6.2.2 Enrollment, Baseline, and/or Randomization

Enrollment

Enrollment date is considered immediately following the signing of the consent form after which the enrollment date is recorded in the case book. The participant will be scheduled for a baseline visit in which she will be requested to fill out the baseline questionnaires and provide half an hour of baseline HR and Respiration measurements and 10 ccs of blood. Following this session, the participant will be randomized to the intervention or comparison group.

Baseline Assessments Visit 1 day 0- can be split in to 2 visits to reduce patient burden (see study schema- figure 1)

T1A

DEMOGRAPHICS AND TRADITIONALISM

- A.** We will be collecting baseline demographic data (age, marital status, children (if yes, and how many), religion, religiosity, education, employment, residence (city, village, etc).
- B.** We will measure ethnocultural differences using the Portrait Values Questionnaire (PVQ-RR), which is a 57-item scale consisting of items designed to measure 19 cultural values⁴³. The scale has been validated in 15 samples across 10 countries (n=6059) including Israel. The mean Cronbach α for the tradition values (which we will use as a covariate to enrich the ethno-cultural differences between Jews and Arabs, was 0.8343.

C. CHOLINERGIC ANTI-INFLAMMATORY PATHWAY

A. HRV: 20 minutes of resting ECG data will be recorded. The participants will be given instructions not to drink coffee or smoke for several hours before the lab visit as well as to sit quietly without talking or moving during the ECG recording.

B. Inflammation: We will collect 10 cc's of blood in order to measure immune dysregulation (pro-inflammatory cytokines IL-6, IL-8, IL-1 β , TNF- α), anti-inflammatory (IL-4, IL-10) and regulatory cytokine (TGF- β).

D. PATIENT REPORTED OUTCOMES (PRO):

A. Depression: The **Center for Epidemiologic Studies-Depression (CES-DR)** scale^{71- 10} ITEM SCALE.

B. Fatigue will be assessed using the Fatigue Symptom Inventory (**FSI**)⁷².

C. Pain: The **Breast Cancer Prevention Trial (BCPT) Symptom Scales**⁷³. The **PROMIS Pain Impact Scale**⁷⁴ measures how much pain interfered with different aspects of life in the past 4 weeks.

T1B

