8.2 Sample Size and Randomization

A power analysis was conducted via Monte Carlo simulation in Mplus showed that a sample size of 240 (120 per condition), provides: (1) >90% power to detect a moderate effect size (Cohen's $d = 0.50$) of treatment on mechanisms, (2) >90% power to detect a moderate association ($r = 0.30$) between mechanisms and symptoms, and (3) >90% power to detect an indirect effect from treatment to symptoms via mechanisms. The sample size will also provide >80% power to detect a moderate effect size for the Condition by Ethno-Cultural group interaction.

Consented participants will be randomized into the Art Therapy or Sham condition using block randomization stratified by site, ethnicity and traditionalism to ensure equal sample sizes between groups over time in each site and in each ethnicity. Permutations of group assignment will be generated in random blocks of 4, 6, and 8 so that staff cannot guess the condition of the final participant as the block size varies. Condition assignment will be stored in sealed, numbered envelopes to be opened consecutively as subjects enroll and the envelopes will designate individuals to the intervention through use of a random numbers table. PI [name] will provide the PhD students with the randomized lists (60 each cohort), who will schedule sessions and make weekly calls to encourage attendance, therefore both will be un-blinded to study assignment. The Research Nurse will collect and enter data, collect bio specimens and manage the database, and thus will be un-blinded after randomization. The research assistant (RA) will remain blinded throughout the study, and will receive lists of participants to call, without knowing which group they are assigned to. Participants will be told they are participating in an "art making" study where they will be assigned to an art making group. Participants will not be told which is expected to be superior.

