8.3 Treatment Assignment Procedures

Consented participants for each cohort will be randomized (PI- [name]) The University statistician will generate numbered envelopes to be opened consecutively as subjects enroll and the envelopes will designate individuals to the intervention through use of a random numbers table. PI [name] will provide the PhD students with the randomized lists (60 each cohort), who will schedule sessions and make weekly calls to encourage attendance and conduct the intervention and thus will be unblinded. The Research Nurse will collect and enter data, collect bio specimens and manage the database, but will remain blinded after randomization. The research assistant will remain blinded throughout the study, and will receive lists of participants

to call, without knowing which group they are assigned to. Participants will be told they are participating in an “art making” study where they will be assigned to either the intervention group or the sham intervention (Mandala) group. Participants will not be told which is expected to be superior.

Table 4: Roles in the study

Title	Blinded to group assignment	Roles	Rambam	Ziv	Beilinson
Research nurse (employee of each hospital).	Yes	Recruit and obtain verbal consent, collect blood.	1	1	1
Research coordinator (employee of each hospital).	Yes	Assist MD in recruiting patients, collect data (questionnaires and HRV), transfer blood to the lab for processing (separation to serum, divide in 4 aliquots and cryopreservation -80)	1	1	1
Art Therapist	No	Conduct intervention groups (8.5 weeks)- Art Therapy and SHAM in Hebrew or Arabic	2	2	2
PhD student	No	Conduct groups, supervise interventionists, assist in fidelity assurance, assist in data analysis.	3		
Laboratory worker	Yes	Conduct inflammatory cytokines analysis.	1		
Research coordinator	Yes	Coordinate between study site, transport frozen serum to lab, input data	1		

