9. DATA COLLECTION AND QUALITY ASSURANCE

9.1 Data Collection Forms

PI [name] will provide the research coordinators with the randomized lists (60 each cohort), who will schedule sessions and make weekly calls to encourage attendance, therefore both will be un-blinded to study assignment. The Research Nurse will collect and enter data, collect bio specimens and manage the database, and thus will be un-blinded after randomization. The research assistant will remain blinded throughout the study, and will receive lists of participants to call, without knowing which group they are assigned to. Signed

consent forms and all study questionnaires will be kept in an administrative office separate from research data and available for audit even when the PI is not. Additional information contained in this case book will be relevant demographic and medical/psychiatric information about the subject obtained during the interview with the site representative. Because this case book will contain personal identifiers and PHI, it will be kept separate from any data gathered as part of the study and will be kept in a locked office.

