11. SUPPLEMENTS/APPENDICES

I. Procedures Schedule Oct. 2018- Sept. 2021.

Table 3: Study Timeline						
Months	1-6	7-12	13-18	19-24	25-30	31-36
Prep/Training	X					
Team mtgs	X4	X4	X2	X1	X2	X6
Intervention		Cohort1	Cohort 2	Cohort 3	Cohort 4	
Data chk**		X		X		
Analysis				X (prelim)		X
Writing/discussion			X			X
Presentation at Conferences						X
Travel	[name] to Israel- Nov. 2018 [name] to Israel Jan 2019					Drs. [name], [name] and [name] to Tucson, AZ- spring/summer 2021
Final cohort begins mo. 25, allows final data mo. 31. **Data check/quality. Balance across arms on factors used in minimization technique will be monitored and adjusted.						

II. Informed Consent Form Template

DEMOGRAPHICS HEBREW-T0

דמוגרפי

אני עני על השאלות הבאות. בשאלות שיש לצד תשובה, אני הקيفי את התשובה המיטיבת לתראר את מצבך. בשאלות שאין לצד אפשרות תשובה, אני השלמי בעצמך:

גיל	ארץ לידה	ישראל	אחר	35-26	45-36	70-46	מעל 70
מצב משפחתי	האם יש לך ילדים?	רווקה	נשואה	גירושה	אלמנה	אחר:	אחר:
השכלה	האם את עבדת?	תיכוןית	לימודי תעודה	אקדמיית – תארים	אקדמיית – תואר ראשון	מתקדמיים	אחר
דת	האם את שולך?	יהודיה	מוסלמית	נוצריה	אחר	אחר	אחר
כיצד הייתה מגדרה את מידת הדתiot שלך?	האם את עוסקת באמנות?	דתיה	חילונית	מסורתית	אחר	כנים, בחוותני, מקצועני	כנים, בחוותני, מקצועני

DEMOGRAPHICS ARABIC T0

فيما يلي عدة أسئلة، يرجى احاطة رقم الإجابة الصحيحة وإكمال المعلومات الناقصة:

كم عمرك؟
 من فوق 70 70-46 45-36 35-26 25-18

1. ارض الولادة: اسرائيل اثيوبيا الاتحاد السوفيت ي سابقا آخر

2. الوضع العائلي: متوجزة ارمل/ة مطلقة مقصولة عازب/ة آخر

1. هل لديك اولاد؟ لا نعم

هل تسكن في: مدينة قرية مستوطنة آخر

1. ما هي درجتك التعليمية؟
 اخر اكاديمية - لقب ثالث اكاديمية - لقب ثالثي طالب/ة او لقب او اول

هل تعمل/ين؟
 الوضع الاقتصادي
 نعم لا اقل من الوسط اعلى من الوسط

الديانة
 يهودي/ة مسلم/ة مسيحي/ة درزي/ة آخر

كيف تعرف نفسك؟
 علماني/ة متدين/ة ارثوذوكسي/ة تقليدي/ة آخر

هل انخرطت في الفن؟
 لا نعم، بطريقة هواة نعم، مهنيا

PVQ-RR F Hebrew T0

המשפטים הבאים מטארים בקצרה אנשים שונים. קראי בבקשתו כל תיאור וחשי עד כמה האדם הזה דומה, או לא דומה לך. סמני X ביריבוע משMAL המתאר עד כמה האדם המתואר דומה לך.

עד כמה אדם זה דומה לך?

מאת דומה לי	דומה לי	די דומה לי	קצת דומה לי	לא דומה לי	בכל לא דומה לי	
	.1. חשוב לה לעצב את השקופותיה באופן עצמאי.					
	.2. חשוב לה שהמדינה שלה תהיה בטוחה ויציבה.					
	.3. חשוב לה לבנות בנעימים.					
	.4. חשוב לה להימנע מהרגיז אנשים אחרים.					

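### The protocol's statements on allocation method, timing, list-holders and blinding conflict and need reconciling; no concealment breach is shown

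*Protocol*

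**What the plan says.** **Method.** Protocol 8.2 stratifies by site, ethnicity and traditionalism, and states: "Permutations of group assignment will be generated in random blocks of 4, 6, and 8". Assignments sit in sealed, numbered envelopes. The Design and Outcomes summary also names permuted blocks, but only for ethnicity and traditionalism, without site. The footnote to Table 3 (section 11), attached to the data-check row, reads: "Balance across arms on factors used in minimization technique will be monitored and adjusted". The SAP does not describe the allocation method, so it does not settle the matter.

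**Timing.** Sections 6.2.2, 8.2 and 8.3 all refer to "numbered envelopes to be opened consecutively as subjects enroll". Section 6.2.2 defines the moment of enrolment: "Enrollment date is considered immediately following the signing of the consent form". The same section then schedules the baseline visit and places randomisation after it.

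**Lists and blinding.** In 9.1 a PI "will provide the research coordinators with the randomized lists (60 each cohort" and the recipients are called un-blinded. In 8.2 and 8.3 the recipients are PhD students. Table 4 gives the hospital research coordinator this role: "Assist MD in recruiting patients, collect data (questionnaires and HRV". Section 6.2.3 and Table 4 list coordinators as blinded. The research nurse is un-blinded in 8.2 and 9.1, but blinded in 6.2.3, 8.3 and Table 4.

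**The concern.** The comparison of art therapy with the mandala group rests on three things: an allocation nobody can foresee or alter, made after baseline, with outcomes collected by staff who do not know the arm. Each is stated somewhere in the protocol, and each is contradicted elsewhere in current text.

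The consequences differ by contradiction. If the footnote is followed, someone may change assignments after inspecting balance, under a rule the protocol does not give. If envelopes are opened at consent, a woman's arm may be known before her baseline measures, from which the SAP calculates change. If 9.1 is followed, the people holding the lists may be the same people who help to recruit and who collect the questionnaires and HRV. Those data carry the emotion-processing and HRV primary outcomes and the symptom outcomes.

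**Working it through.** **1. The plan's own figure.** Section 8.2 states "a sample size of 240 (120 per condition" and ">90% power to detect a moderate effect size" at d = 0.50. Alpha is not stated, so I assume 0.05 two-sided. The Mplus inputs are not given, so this is a plain two-group normal approximation that ignores repeated measures and grouping.

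- Power = Φ(d / √(1/n₁ + 1/n₂) − 1.96)
- 120/120: Φ(0.5/√(2/120) − 1.96) = Φ(3.873 − 1.960) = 97.2%, consistent with the stated figure
- 105/135: Φ(0.5/0.1301 − 1.96) = Φ(1.883) = 97.0%
- 90/150: Φ(0.5/0.1333 − 1.96) = Φ(1.790) = 96.3%

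Uneven arms would not threaten the power for this main effect. The point is about bias and about which procedure staff follow.

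**2. Method.** A block sequence in sealed envelopes is complete before the first woman is allocated. Minimisation computes each assignment from the women already entered, so it cannot be pre-filled. Nothing in 8.2 can be adjusted without departing from 8.2. Table 3 puts the data checks in months 7–12 and 19–24, and cohorts run through months 25–30, so later cohorts would still be open to any adjustment. No minimisation factors, algorithm or random element are given anywhere.

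**3. Timing.** Combining the envelope wording with the definition of enrolment in 6.2.2 gives opening at consent. The explicit randomisation sentences in 6.2.2 give opening after the baseline visit. Section 6.2.2 also allows baseline to be split over two visits (T1A and T1B, with emotion processing in T1B), so the interval between consent and complete baseline can be real.

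**4. Lists and blinding.**

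| Place | Lists go to | Coordinators | Research nurse |
|---|---|---|---|
| 6.2.3 | not stated | blinded | blinded |
| 8.2 | PhD students | not stated | un-blinded |
| 8.3 text | PhD students | not stated | blinded |
| Table 4 | not stated | blinded (hospital and central) | blinded |
| 9.1 | coordinators | un-blinded | un-blinded |

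Section 9.1 does not say which coordinator it means. Table 4 has a hospital type, who helps to recruit and collects data, and a central type with no recruiting role. Both are listed as blinded, so 9.1 conflicts with Table 4 on either reading.

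**5. Strata.** Traditionalism has no named stratifying measure, number of levels or cut-off. Section 6.2.2 calls the PVQ-RR tradition values a covariate.

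**The case against.** Much can be said for the protocol, and most of it limits how far the point may be taken.

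- *A reader might infer one unstratified envelope series.* No section says so. Section 8.2 puts stratified blocks, envelopes and a random numbers table in one procedure, and 6.2.2 and 8.3 give the envelope sentence without repeating the strata. Consecutive envelopes within each stratum fit all three. The gap is only that a series per stratum is not stated. Calculations of imbalance under simple randomisation would describe a scheme the protocol does not specify.
- *A reader might infer that women are allocated before baseline.* Section 6.2.2 says the opposite in explicit sentences, and the schedule in 6.1 puts consent, enrolment/randomisation and baseline measures all on Day 0. The envelope wording is loose. It still contradicts the explicit text and appears in three sections.
- *A reader might infer that stratification by traditionalism is impossible at consent.* That would follow if the PVQ-RR defined the stratum, which is not stated. The demographics form has a religiosity item with a traditional option, and 6.1 lists demographics at screening.
- *A reader might infer that recruiters hold the future sequence.* Only 9.1 names coordinators, and the lists serve to schedule sessions and make attendance calls, which suits women already randomised. Concealment cannot be confirmed from the text, but a breach is not shown.
- *Minimisation appears once, in an appendix footnote, and what is adjusted is undefined.* Minimisation with a random element is also a legitimate method. Both are true, but the footnote is current text that tells staff to act, and 8.2 does not allow that action.

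**Conclusion.** Wrong as written. Three contradictions bear on bias: fixed blocks against adjusted minimisation, envelope opening at consent against randomisation after baseline, and un-blinded coordinators holding lists against blinded coordinators. Two lesser ones are the omission of site from the strata in the summary and the nurse's blinding status.

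No figure can be put on the bias, because the documents do not say which version staff will follow or whether the lists contain future assignments. The risk is conditional: following 9.1 could unblind staff who recruit and collect outcomes, and following the Table 3 footnote could alter allocation after balance has been inspected. The sample size does not depend on this. Under the assumed two-sided 0.05 level, power for d = 0.50 stays between 96% and 97% across the splits examined.

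**What to change.** Make one set of wording changes:

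1. Keep the 8.2 scheme as the only method, with a separate envelope sequence for each stratum, generated and held by the University statistician. Add site to the Design and Outcomes summary so that it agrees.
2. Name the traditionalism measure and its levels, using one available before allocation, or drop it as a stratum.
3. In 6.2.2, 8.2 and 8.3, have each envelope opened after completion of baseline assessments, not at enrolment.
4. In the Table 3 footnote, delete the reference to minimisation and the statement that balance will be adjusted. Balance is then monitored and reported only.
5. In 9.1, name PhD students as the recipients, and state that the lists contain only women already randomised.
6. Make the blinding status of nurses and coordinators agree across 6.2.3, 8.2, 8.3, Table 4 and 9.1.

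The cost is small. The statistician already generates the envelopes. The added work is separate envelope sets, or contact with the statistician at each release: 3 sites × 2 ethnicities = 6 sets, or 12 if traditionalism is kept at an assumed two levels.

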10. עד כמה, במהלך השבוע האחרון העיפות הפריעו להנאה מחייב.

[figure not shown]
11. עד כמה, במהלך השבוע האחרון העיפות הפריעו לרמת הפעילות הכלכלית שלך.

12. כמה ימים, במהלך השבוע האחרון חשת עייפות בחלק כלשהו של היום.

[figure not shown]
13. צייני איזה חלק מהיום במומצע, חשת עייפות במהלך השבוע האחרון.

[figure not shown]
FSI ARB T0, T1, T2

بكل جملة من الجمل الآتية، أحيطي بدائرة حول الرقم الذي يصف شعورك بدقة.

[figure not shown]
1. مستوى التعب الذي شعرت به في اليوم الأكثر متعب خلال الأسبوع الماضي(الأخير).

2. مستوى تعいく في اليوم الاقل تبعاً خلال الاسبوع الاخير

- ### 3. معدل مستوى التعب خلال الأسبوع الأخير

[figure not shown]
- #### ٤. مستوى تعادل الازن

[figure not shown]
- ## 5. درجة تأثير التعب بشكل سلبي على نشاطك اليومي في الأسبوع الأخير

[figure not shown]
6. درجة تأثير التعب بشكل سلبي على قدرتك بالاستحمام او اللبس بالأسبوع الاخير

[figure not shown]
7. حتى اي (لأي) درجة أثر التعب بشكل سلبي على نشاط عملك المعتاد خلال الاسبوع الاخير(يشمل العمل خارج البيت وداخل البيت ايضاً).

[figure not shown]
8. حتى اي (لأي) درجة أثر التعب بشكل سلبي على قدرتك في التركيز خلال الاسبوع الاخير

9. حديي, حتى اي درجة أثر التعب على علاقائك مع الاخرين خلال الاسبوع الاخير

[figure not shown]
10. حتى اي درجة, أثر التعب بشكل سلبي على متعتك بالحياة في الاسبوع الاخير

[figure not shown]
تأثير قوي جداً

لم يؤثر بالمرة

11. حتى اي درجة، أثر التعب بشكل سلبي على مستوى نشاطك العام في الاسبوع الاخير

12. كم يوم من ايام الاسبوع الاخير شعرت متعبة بجزء معين من اليوم

13. حدد ايء جزء من اليوم بال معدل، شعرت متعبة خلال الاسبوع الاخير

BCPT- HEB T0, T1, T2

נחנו מუוניינים לדעת עד כמה סבלת **ב-4 השבועות האחרונים מהבעיות המתוארות בטבלה**. אנא סמי מספר אחד בכל שורה. אם אין לך את הבעיה בכלל, אז צייני "בכלל לא".
במשך ארבעת השבועות האחרונים עד כמה הפריעו לך:

BCPT ARB T0, T1, T2

نريد أن نعرف مدى المعاناة التي تعرضت لها خلال الأسابيع الأربع الماضية من المشكلات الموضحة في الجدول. يرجى وضع علامة على رقم واحد في كل سطر. إذا لم تكن لديك المشكلة على الإطلاق، فيمكنك الإشارة إلى "لا على الإطلاق". خلال الأسابيع الأربع الماضية، ما مدى ازعاج كل من:

بأقصى حد	كثير جدا	باعتدال	قليل	لا على الإطلاق	
4	3	2	1	0	1. موجات الحرارة
4	3	2	1	0	2. غثاء
4	3	2	1	0	3. قيء
4	3	2	1	0	4. سلس البول أثناء الضحك أو البكاء
4	3	2	1	0	5. سلس البول في وقت آخر
4	3	2	1	0	6. جفاف المهبل
4	3	2	1	0	7. ألم أثناء الجماع
4	3	2	1	0	8. ألم عام في الجسم
4	3	2	1	0	9. ألم في المفاصل
4	3	2	1	0	10. تصلب العضلات
4	3	2	1	0	11. زيادة بالوزن
4	3	2	1	0	12. عدم الرضا عن مظهر جسدي
4	3	2	1	0	13. تسيان
4	3	2	1	0	14. التعرق الليلي
4	3	2	1	0	15. صعوبة في التركيز
4	3	2	1	0	16. ذهني يتشوش بسهولة
4	3	2	1	0	17. تورم في الذراع (سرطان الغدد الليمفاوية)
4	3	2	1	0	18. صعوبة في حركة اليد من جهة الجراحة- العملية.
4	3	2	1	0	19. إفرازات مهبلية
4	3	2	1	0	20. نزيف مهبلوي
4	3	2	1	0	21. الحكة التناسلية أو تهيج
4	3	2	1	0	22. نقص القوى- الطاقة
4	3	2	1	0	23. تعب-ارهاق
4	3	2	1	0	24. عدم الاهتمام بالعلاقات الجنسية
4	3	2	1	0	25. متعة قليلة من العلاقة الجنسية

T0, T1, T2 PROMIS HEB ARB

HEB T0, T1, T2 LEAS

הנחיות למשתף/ת

כעת נתאר בפניך מספר מצבים. אנה תאר/י כיצד להערכתך הייתה מרגישה/ה בכל אחד מהמצבים. את/ה יכול/ה לענות בתשובה קצרה או ארוכה, לפי מה שנחוץ לך על מנת לבטא כיצד הייתה מרגישה/ה. **הדרישה היחידה היא שתשתמש/י בתשובהך במילה "Marginish/ה".** בכל אחד מהמצבים מוזכר אדם נוסף. תאר/י בבקשתו גם מה את/ה חושבת שהאדם האחר ירגיש.

- שכн/ה מבקש/ת ממך לתקן פריט ריהוט. בזמן השcn/ה מתבונן/ת, את מתחילה לדפוק מסמר אבל מפספסת ופוגעת באצבעך.
כיצד את מרגישה?

כיצד השcn מרגיש?

- את הולכת במדבר עם מדריך/ה. אзолו לכם המים לפני שעות. לפי המפה של המדריך/ה, מקור המים הקרוב הוא בעוד שני ק"מ.
כיצד את מרגישה?

כיצד המדריך/ה מרגישה?

3. מישום מישמי אהובה עושה לך עיסוי גב לאחר שחזרת מיום עבודה קשה. כיצד את מרגישה?

כיצד האחר מרגיש?

4. את משתתפת בתחרות ריצה יחד עם חבר/ה לאחר שהתאמנו/ן יחד תקופה ארוכה. כאשר את קרובה لكו הסיום, את מעקמת את الكرסול, נופלת על האדמה, ואת לא מסוגלת להמשיך.

איך את מרגישה?

איך החבר/ה שלך מרגיש/ה?

5. את מטיילת בארץ זורה. מכיר/ה הערה משפילה בנוגע לארץ המוצא שלך.

כיצד את/ה מרגיש/ה?

כיצד המכיר/ה שŁק מרגינש/ה?

6. בעת שאת נסעת על גשר חבלים, את רואה אדם עומד מעבר למעקה, מביט מטה אל המים. **כיצד את מרגישיה?**

כיצד האדם الآخر מרגיש?

7. אהובך/תך שב/ה הביתה לאחר מספר שבועות. כשהוא/היא פותח/ת את הדלת... כיצד את מרגישה?

כיצד אהובך/תך מרגיש/ה?

8. המנהל/ת אומר/ת לך שהעובדת שלך לא מספיק טובה וشعלייך להשתפר. כיצד את מרגישה?

כיצד המנהל/ת מרגישה/ה?

9. את עומדת בתור בנק. האדם לפניך ניגש לדלפק ומתחילה בעסקה מורכבת שצפוייה להמשך זמן רב. כיצד את מרגישה?

כיצד האדם לפניך מרגיש?

10. את ובן/בת הזוג שלך נסעים הביתה מערב בילוי עם חברים. כשאתם פונים לרחוב מגוריכם את רואה רכבי כיבוי אש ליד ביתכם. כיצד את מרגישה?

כיצד בן/בת הזוג מרגיש/ה?

11. עבדת קשה על פרויקט במשך מספר חודשים. מספר ימים לאחר הגשתו, המנהלת/עovere/ת ואומר/ת לך שעשית עבודה מצוינת.

כיצד את מרגישה?

כיצד המנהלת/ת שלך מרגיש/ה?

12. את מקבלת שיחת טלפון לא צפואה מרופאה/ה המודיע/ה לך שאםך נפטרה.

כיצד את מרגישה?

כיצד הרופא/ה מרגיש/ה?

13. את אומרת לחבר/ה שחש/ה בודד/ה שהוא/היא יכול/ה להתקשר אליו בכל זמן שהוא/היא חש/ה צורך לדבר. הוא/היא מתקשר/ת אליו ארבע פעמיות בז'ור.

כיצד את מרגישה?

כיצד החבר/ה שלך מרגיש/ה?

14. רופא/ת השינויים אומרת לך שיש לך מספר חורים וקובע לך תור נוסף.

כיצד את מרגישה?

כיצד רופא/ת השינויים מרגיש/ה?

15. אדם שהיה ביקרתי כלפי עבר נותן לך מחמהה.

כיצד את מרגישה?

כיצד האדם الآخر מרגיש?

16. הרופא אמר כי עליך להימנע מאוכל שמן. חבר/ה חדש/ה בעבודה מתקשר/ת להגיד שהוא/היא יוצאת לאכול פיצה ומזמין/ה אותה להצטרף.

כיצד את מרגישה?

כיצד החבר/ה מרגיש/ה?

17. את וחבר/ה מחליטים להשקיע יחד כסף על מנת להתחיל עסק חדש. מספר ימים לאחר מכן, את מתקשרת לחבר/ה ומגלה שהוא/היא שינה/תיה את דעתו/ה.

כיצד את מרגישה?

כיצד החבר/ה מרגיש/ה?

18. את מוכרת פריט אהוב عليك על מנת לкупות מותנה יקרת ערך לבן/בת הזוג שלך. כשאת מעניקה לו/לה את המותנה הוא/היא שואל/ת האם מכרת את הפריט יקר הערך.

כיצד את מרגישה?

כיצד בן/בת הזוג מרגיש/ה?

19. את מתאהבת במשהו/י גם מושכ/ת וגם חכמ/ה. לא אכפת לך שמצוות הכספי לא טוב, הכנסתך מספקת. כשאתם מתחילהים לדבר על חתונה, את/ה מגלה שהוא/היא בעצם מגע/ה ממשפחה מאוד עשרה. הוא/היא לא רצה/תיה שהדבר יתגלה מנקודת חיש שיתעניינו בו/ה רק בגלל הכספי.

כיצד את מרגישה?

כיצד הוא/היא מרגיש/ה?

20. את וחברך/תך הטוב/ה ביותר עוסקים באותו תחום העבודה. יש פרס שנתי שניתן עבור הביצועים הטובים ביותר. שנייכם/שתיכן עבדתם/ן קשה עבור הפרס. ערבות אחד מכריזים על הזוכה :חברה/ה שלך.

כיצד את מרגישה?

כיצד חבר/ה שלך מרגיש/ה?

LEAS ARB T0, T1, T2

التعليمات:

من فضلك اوصف/ي ماذا سيكون شعورك في هذه الحالات. الشرط الوحيد هو أن تستعمل/ي كلمة "أشعر" في اجاباتك.
بإمكانك أن تختصر/ي أو تطيل/ي بالإجابة طالما كان ذلك ضرورياً للتعبير عن كيفية شعورك.
في كل حالة، هناك شخص آخر مذكور. يرجى أن توضح/ي ماذا تعتقد/ين انه سوف يشعر ايضاً.

1. يطلب/مطلوب منك أحد الجيرانات أن تصلح/ي له قطعة من الأثاث. وعندما كان/ات هو/هي ينظر/تنظر إليك
بدأت/ي بدق المسمار ولكنك أصمعته وضررت/ي أصبعك. كيف سيكون شعورك؟ وكيف سيشعر/استشعر
الجار الجار؟؟

2. بعد عودتك من يوم شاق في العمل شخص مقرب محب يأتي ليلاً لك ظهرك. كيف سيكون شعورك؟ وكيف
سيشعر هذا الشخص؟

3. وأنت تقود/ي السيارة على جسر معلق، هناك شخص يقف بالجانب الآخر من الدراجين وينظر الى الماء في
الأسفل، كيف سيكون شعورك؟ وكيف سيكون شعور الشخص؟

4. رئيس/رئيسة في العمل يخبرك بأن عملك كان غير مقبول ويحتاج الى تحسين. كيف سيكون شعورك؟ وكيف
سيكون شعوره؟؟؟

5. وأنت تقف لتنظر/ي دورك في البنك. الشخص الذي أمامك يتقدم الى الشباك ويبداً بمعاملة معقدة جداً. كيف
سيكون شعورك؟ وكيف سيكون شعور الشخص الذي أمامك؟

6. كنت قد عملت بجد على مشروع لعدة أشهر. بعد عدة أيام من تقديمك، رئيسك/رئيسك في العمل يقف اتفق ليخبرك/تتدرك بأن عملك كان ممتازاً. كيف سيكون شعورك؟ كيف سيكون شعور رئيسك/رئيسك؟

7. يخبرك/تتدرك طبيب/ة الأسنان بأن لديك عدّة تجاويف ويعينك/تعين لك موعد لزيارة قادمة. كيف سيكون شعورك؟ كيف سيكون شعور طبيب/ة الأسنان؟

8. أخبرك/أدرك طبيب/ة طبيتك/طبيتك بتجنب الأطعمة الدهنية. زميلك/زميلتك الجديد/ة في العمل يدعوك/تدعوك لتناول البيتزا. كيف سيكون شعورك؟ كيف سيكون شعور زميلك/زميلتك؟

9. أنت وصديق/ة تتفقان لاستثمار المال معاً للبدأ بمشروع تجاري جديد. بعد عدة أيام تتصل بهما/ا لتعلم بأنهما/ا غير رأيهما/ا. كيف سيكون شعورك؟ كيف سيشعر صديقك؟

10. وقعت أي بالحب مع أحدهم بشخصية جذابة وذكية. على الرغم من أن هذا الشخص حاليه المادية ليست جيدة، هذا ليس مهم بالنسبة لك—فذلك كاف. عندما تبدعوا بالحديث عن الزواج تعلم بأنه/ا من عائلة غنية للغاية. وهو/هي لم يخبرك/تدرك بسبب مخاوفه/ا بأن الناس سوف يهتمون به/ا لأجل ماله/ا. كيف سيكون شعورك؟ كيف سيشعر استشعر هو/هي؟

11. انت تمشي في الصحراء مع مرشد. نفذت معكم المياه من قبل ساعة. حسب خارطة المرشد اقرب بئر يبعد عنكم 3 كيلومتر. كيف سيكون شعورك؟ كيف سيكون شعور المرشد؟

12. انت ترکض این في سباق مع صديق/ة تدریت معه/ا البعض الوقت. وانت تقترب اين من خط النهاية، يلتوي کاحلك، وتسقط على الأرض، ولا تقدر على الاستمرار. كيف سيكون شعورك؟ كيف سيكون شعور صديقك/صديقتك؟

13. انت مسافرا في بلد اجنبي. شخص من احد معارفك يقول اتقول تصريحات مهينة لبلادك الأصلي. كيف سيكون شعورك؟ كيف سيشعر الشخص؟

14. حبيبك/حبيبك ذهب/ت لعدة أسابيع وآخر انتى/انت الى المنزل. وهو/وهي يفتح/تفتح الباب...كيف سيكون شعورك؟ كيف سيكون شعوره؟

15. انت وزوجك/زوجتك رجعتم في السيارة الى المنزل بعد سهرة مع الأصدقاء، وعند اقترابكم من حيكم ترون سيارات اطفاء مصطفه بالقرب من منزلكم. كيف سيكون شعورك؟ كيف سيكون شعور زوجك/زوجتك؟

16. تتلقى مكالمة هاتفية غير متوقعة بعيدة المدى من طبيب/ة يخبرك بأن امك قد توفت. كيف ستشعر؟
كيف سيشعر الطبيب/ة؟

17. تخبر صديقك/صديقتك الذي/التي يشعر/تشعر بالوحدة انه/ا بامكانه/ا الاتصال بك بأي وقت هو/هي يحتاج/تحتاج الى التحدث. في احدى الليالي يتصل/تتصل بك الساعة الرابعة قبل الفجر. كيف ستشعر؟ كيف سيشعر/ستشعر صديقك/صديقتك؟

18. احدهم احدهن كان/ت ينتقدك/تنتقدك في الماضي, يقدم/تقدّم لك اطراء. كيف ستشعر؟ كيف سيشعر الشخص؟

19. تبيعين شيء غالٍ عليك من ممتلكاتك لكي تشتري هدية ثمينة لزوجتك/زوجك. عندما تعطيها/تعطيه اياها تسألك/يسألك ان كنت قد بعت غرض لك. كيف ستشعر؟ كيف سيشعر/سيشعر زوجتك/زوجك؟

20. انت وصديقك/صديقتك المفضل/ة في نفس خط العمل. هناك جائزة سنوية تقدم لأفضل اداء للسنة. كلّاكم عملتما جاهدا للفوز بالجائزة. في احد الليالي اعلنوا عن الفائز: صديقك/صديقتك. كيف ستشعر؟ كيف سيشعر/ستشعر صديقك/صديقتك؟

COPE EAC HEB T0, T1, T2

אנא קראי כל משפט, והעריכי באיזו מידת הגד מעתישת/ה כל דרכם תמודדות עם הוויית סרطن השד בארבעת השבועות האחרוןינו:

מספרה לענות	אני עשה זאת לעתים לרובות	אני עשה זאת במידה בינונית	אני עשה זאת מעט	אני לא עשה זאת	
8	4	3	2	1	1. אני לומדת מההתקנות עם המצב
8	4	3	2	1	2. אני לוקחת זמן להבין איך אני באמת מרגישה
8	4	3	2	1	3. אני מרכזת את כוחותי כדי לעשות משהו
8	4	3	2	1	4. אני מודה בפמי עצמי שאני יכול/ה לטפל במצב וmpsik/ה לנסות
8	4	3	2	1	5. אני משלימה עם העבודה שווה קרה ושה לא ניתן לשינוי
8	4	3	2	1	6. אני מנסה להתייעץ עם מישוה לגבי מה כדאי לעשות
8	4	3	2	1	7. אני קובעת הכנית פעולה
8	4	3	2	1	8. אני מעמיקה ברגשותי כדי להבין אותן בצורה יסודית
8	4	3	2	1	9. אני פועלת כדי לשפר את המצב
8	4	3	2	1	10. אני מנהגת כאלו זה כלל לא קרה
8	4	3	2	1	11. אני מנסה לקבל עזרה ויעוץ מאחרים
8	4	3	2	1	12. אני אומרת לעצמי ש "זה לא באמת"
8	4	3	2	1	13. אני לוקחת זמן כדי לבטא את רגשותי
8	4	3	2	1	14. אני מעמידה פנים כאלו זה לא קרה
8	4	3	2	1	15. אני לומדת לחיות עם זה
8	4	3	2	1	16. אני חושבת הרבה על הצעדים שעלי לנ��וט
8	4	3	2	1	17. אני מרצה לעצמי להביע את רגשותי
8	4	3	2	1	18. אני מנסה לראות את הדברים באור היבוי יותר
8	4	3	2	1	19. אני מקבלת נחמה והבנה ממישוה
8	4	3	2	1	20. אני מफש/ת מהו טוב בדברים שקרו
8	4	3	2	1	21. אני מרגישה חופשיה להביע את רגשותי
8	4	3	2	1	22. אני מקבלת תמיינה רגשיות מאחרים
8	4	3	2	1	23. אני מסרב/ת להאמין שזה קרה
8	4	3	2	1	24. אני מתרגלת לרעין שזה קרה
8	4	3	2	1	25. אני מרגישה שהרגשות שלי תקפים וחשובים
8	4	3	2	1	26. אני חולמת בהקיזע על דברים אחרים
8	4	3	2	1	27. אני מותרת על הניסיון להתמודד עם זה
8	4	3	2	1	28. אני פונה לפעילויות חלופיות כדי להסיח את דעתך מהמצב
8	4	3	2	1	29. אני מדברת על רגשותי בחופשיות
8	4	3	2	1	30. אני מותרת על הניסיון להתמודד
8	4	3	2	1	31. אני ישנה יותר מבדרך כלל כדי לחשב על זה פחות
8	4	3	2	1	32. אני מכירה ברגשותי
8	4	3	2	1	33. אני מנסה לצמוח כאדם כתוצאה מהחויה
8	4	3	2	1	34. אני מפחיתה את כמות המאמצים שאני משקיעה בהתמודדות
8	4	3	2	1	35. אני פונה לעבודה או פעילויות אחרות כדי להסיח את דעתך
8	4	3	2	1	36. אני מקבלת את זה שזה מה שקרה וזה לא ניתן לשינוי

COPE ARB T0, T1, T2

خلال الأسابيع الأربع الماضية: لطفاً، اقرئي كل جملة وحاولي تقييم درجة استعمالك لكل طريقة تأقلم مع تجربة سرطان الثدي.

أرفض الإجابة	أفعل هذا بشكل كبير	أفعل هذا بشكل معتدل	أفعل هذا بشكل قليل	لا أفعل هذا	
					1. أنا اتعلم من تجربتي مع الوضع.
8	4	3	2	1	2. أخذ بعض الوقت لكي أفهم ماذا أشعر بالفعل.
8	4	3	2	1	3. أركز كل طفاطي لكي انفذ امر معين.
8	4	3	2	1	4. أنا اعترف لنفسي بأنني لا أستطيع ان اتعامل مع الموقف وأتوقف عن المحاولة.
8	4	3	2	1	5. أنا اقبل حقيقة أن الأمر حدث ولا يمكن تغييره.
8	4	3	2	1	6. أحاول استشارة شخص ما حول ما يجب علي فعله.
8	4	3	2	1	7. أنا أضع خطة عمل.
8	4	3	2	1	8. أنا اعمق بمشاعري لكي أفهمها جيداً.
8	4	3	2	1	9. أنا أعمل لكي أحسن الوضع.
8	4	3	2	1	10. أنا اتصرف كأن الامر لم يحدث ابداً.
8	4	3	2	1	11. أحاول ان اتفقى مساعدة وإستشارة من الآخرين.
8	4	3	2	1	12. أقول لنفسي أن "هذا غير صحيح".
8	4	3	2	1	13. أخذ بعض الوقت لكي اعبر عن مشاعري.
8	4	3	2	1	14. انتظاره كأن الأمر لم يحصل.
8	4	3	2	1	15. اتعلم ان اتعايش مع الأمر.
8	4	3	2	1	16. افكرا كثيرا حول الخطوات التي يتوجب على اتخاذها.
8	4	3	2	1	17. اسمح لنفسي ان اعبر عن مشاعري.
8	4	3	2	1	18. أحاول ان أرى الأمور بصورة إيجابية أكثر.
8	4	3	2	1	19. احصل على الراحة- القهقهة والاحتواء من شخص ما.
8	4	3	2	1	20. ابحث عن امر جيد بالأمور التي حصلت.
8	4	3	2	1	21. اشعر بحرية التعبير عن مشاعري.
8	4	3	2	1	22. احصل على دعم عاطفي من الآخرين.
8	4	3	2	1	23. ارفض التصديق بان هذا حصل.
8	4	3	2	1	24. اعتدت على فكرة ان الامر قد حصل.
8	4	3	2	1	25. أنا اشعر بان مشاعري صحيحه-ملائمه و مهمه.
8	4	3	2	1	26. احلم بان استيقظ على امور اخرى.
8	4	3	2	1	27. اتخلى عن محاولة التعامل- الاعتياد مع هذا الامر.
8	4	3	2	1	28. اتوجه لفعاليات وانشطة بديلة لصرف نفسي -الهني نفسي عن الوضع.
8	4	3	2	1	29. أنا اتحدث عن مشاعري بحرية.
8	4	3	2	1	30. اتخلى عن محاولة التأقلم.
8	4	3	2	1	31. انام لوقت اطول من المعتاد لكي افكرا بالامر اقل.
8	4	3	2	1	32. أنا أعي- اعرف مشاعري.
8	4	3	2	1	33. أحاول ان أضخم وانمو من هذه التجربة.
8	4	3	2	1	34. أقوم بتنقيل المجهود الذي ابذله واستثمره في التأقلم.
8	4	3	2	1	35. اتوجه للعمل او فعالية اخرى لكي اشتغل واصرف تفكيري بأمور اخرى.
8	4	3	2	1	36. اتفق الامر بأن هذا ما حدث ولا يمكن تغييره.

T0 T1 T2 שאלון קבלה רגשית

אנו צייני (על ידי הקפה בעיגול) עד כמה כל הצהרה מתארת את יחסך לרגשותייכך בצורה מיטבית. 0 = בכלל לא כמוני ; 100 = בדיקך כמוני.

1. אני מנסה להבין בדיקך מה קורה עם הרגשות שלי, מכיוון שאני רוצה לעזור לעצמי

100 100 90 80 70 60 50 40 30 20 10 0

2. נוח לי עם רגשותייכך כפי שהם, למורות שאני יודעת שאינם "מושלמים"

100 100 90 80 70 60 50 40 30 20 10 0

3. אני נותנת לעצמי להרגיש שמחה ושבעת רצון עם רגשותייכך, בדיקך כפי שהם

100 100 90 80 70 60 50 40 30 20 10 0

4. אני עובדת ומתחמת על פיתוח רגשות בעלי ערך

100 100 90 80 70 60 50 40 30 20 10 0

5. אני מוקירה את רגשותייכך בצורה רכה ואוחבת

100 100 90 80 70 60 50 40 30 20 10 0

6. אני מתייחסת לרגשותייכך בקלות ובאופן טבעי

100 100 90 80 70 60 50 40 30 20 10 0

7. אני מאוד נהנית מהרגשות שלי

100 100 90 80 70 60 50 40 30 20 10 0

8. אני מעריכה את רגשותייכך, בצורה עדינה וחמה, בדיקך כפי שהם

100 100 90 80 70 60 50 40 30 20 10 0

9. אני משחררת בנוחות את רגשותייכך מכיוון שהם משקפים את העצמי הפנימי והעמוק

100 100 90 80 70 60 50 40 30 20 10 0

10. אני מטפלת ושם לה לרגשותייכך בנוחות

100 100 90 80 70 60 50 40 30 20 10 0

11. אני משקיעה הרבה כוחות להבין את רגשותייכך ולבחרו איך להתמודד איתן

100 100 90 80 70 60 50 40 30 20 10 0

12. אני מבינה ומחבבת את רגשותייכך בדיקך כפי שהם

100 100 90 80 70 60 50 40 30 20 10 0

13. אני מרצה לעצמי להיות מחוברת לרגשותייכך מכיוון שהוא טוב עבורי

100 100 90 80 70 60 50 40 30 20 10 0

שאלון קבלת רגשיות ערבית TO,T1,T2

لطفاً، أحيط بدائرة الى أي مدى تصف كل عبارة علاقتك بمشاعرك بأفضل شكل . 0=لا يمثلي على الاطلاق؛ 100=يمثلني تماماً.

1. أحاول أن أفهم بالضبط ماذا يحدث مع مشاعري، بحيث أريد أن أساعد نفسي.

100 90 80 70 60 50 40 30 20 10 0

2. أنا مررتاحة مع مشاعري كما هي، على الرغم من أنني أعي بأنها غير "مثالية"

100 90 80 70 60 50 40 30 20 10 0

3. أعطي نفسي ان اشعر بالسعادة والرضا مع مشاعري، بالضبط كما هي.

100 90 80 70 60 50 40 30 20 10 0

4. أنا اعمل واتمرن على تطوير مشاعر ذات قيمة.

100 90 80 70 60 50 40 30 20 10 0

5. اعتز بمشاعري بشكل لطيف ومحب.

100 90 80 70 60 50 40 30 20 10 0

6. اتعامل مع مشاعري ببساطة وبشكل طبيعي.

100 90 80 70 60 50 40 30 20 10 0

7. أنا استمتع كثيراً من مشاعري.

100 90 80 70 60 50 40 30 20 10 0

8. أنا أقدر مشاعري، بشكل لطيف ودافئ، تماماً كما هي.

100 90 80 70 60 50 40 30 20 10 0

9. أنا أطلق مشاعري بكل راحة من منطلق أنها تعكس حقيقي ونفسائي بشكل عميق.

100 90 80 70 60 50 40 30 20 10 0

10. أنا اعتنى وانتبه لمشاعري بشكل مريح.

100 90 80 70 60 50 40 30 20 10 0

11. ابذل طاقات كبيرة لكي أفهم مشاعري واختار كيف اتعامل معها.

100 90 80 70 60 50 40 30 20 10 0

12. أنا أفهم وأحب مشاعري واجدها مناسبة تماماً كما هي.

100 90 80 70 60 50 40 30 20 10 0

13. أسمح لنفسي بالتواصل مع مشاعري لأنه جيد بالنسبة لي.

100 90 80 70 60 50 40 30 20 10 0
